#### 7.4 Neurotoxicity

While CNS toxicity is a clearly defined syndrome associated with T-cell-based therapies, it is rare and generally not believed to be a toxicity associated with NK cell therapies. Neurotoxicity was reported in one trial of adoptively transferred NK cells given with subcutaneous IL-15 but the mechanism of the toxicity was not well defined (Cooley 2019). Nervous system toxicities following CD19 CAR-T therapy is characterized by encephalopathy, confusion, delirium, aphasia, obtundation, and seizures (Yescarta USPI 2017; Kymriah USPI 2018). Cases of cerebral edema have also been reported (Brudno 2016).

If signs and symptoms of CNS toxicity occurs, it will be graded as outlined in the ASTCT consensus grading system for ICANS (Lee 2019, Section 10); management should follow current recommendations for CAR-T-cell therapies (Neelapu 2018).

If the patient develops neurological toxicity for which cerebrospinal fluid (CSF) analysis is performed, in addition to standard clinical testing, the sample will be tested for Human Herpes Virus (HHV 6&7) since HHV6 and HHV-7 may cause

neurological toxicity in an immunocompromised host which may go unrecognized. In addition, quantitative testing in blood for HHV6 and HHV7 in the context of neurotoxicity will be done. Neurotoxicity must be monitored as per the Section 8.1 using the ASTCT guidelines for grading ICANS (Section 10) based on the immune cell-associated encephalopathy (ICE) score. Determinants of the ICE score are outlined below.

#### ICE Score Determination:

- Orientation: Orientation to year, month, city, hospital: 1 point each for maximum of 4 points
- Naming: Name 3 objects (e.g., point to clock, pen, button): 1 point each for maximum of 3 points
- Following commands: (e.g., show me 2 fingers or close your eyes and stick out your tongue): 1 point
- Writing: Ability to write a standard sentence (e.g., our national bird is the bald eagle): 1 point

Table 2 ASTCT Immune Effector Cell-Associated Neurotoxicity Syndrome Grading a							
Neurotoxicity Domain	Grade 1	Grade 2	Grade 3	Grade 4			
ICE Score b	7–9	3–6 0–2		0 (subject is unarousable and unable to perform ICE.)			
Depressed level of consciousness c	Awakens spontaneously	Awakens to voice	Awakens only to tactile stimulus	Subjects is unarousable or requires vigorous or repetitive tactile stimuli to arouse. Stupor or coma.			
Seizure	N/A	N/A	Any clinical seizure Focal/generalized that resolves rapidly; or Non-convulsive seizures on EEG that resolve with intervention	Life-threatening prolonged seizure (>5 minutes); or Repetitive clinical or electrical seizures without return to baseline in between.			
Motor Findings d	N/A	N/A	N/A	Deep focal motor weakness such as hemiparesis or paraparesis			

• Attention: Count backwards from 100 by ten: 1 point

Table 2 ASTCT Immune Effector Cell-Associated Neurotoxicity Syndrome Grading a							
Neurotoxicity DomainGrade 1Grade 2Grade 3Grade 4							
Raised ICP/ Cerebral Edema	N/A	N/A	Focal/local edema on neuroimaging e	Diffuse cerebral edema on neuroimaging; Decerebrate or Decorticate posturing; or Cranial nerve VI palsy; or Papilledema; or Cushing's triad			

ASTCT, American Society for Transplantation and Cellular Therapy; CTCAE, Common Terminology Criteria for Adverse Events; ICANS, immune effector cell-associated neurotoxicity syndrome; ICE, immune effector cell-associated encephalopathy; ICP, intracranial pressure; EEG, electroencephalogram; N/A, not applicable.

- a ICANS grade is determined by the most severe event (ICE score, level of consciousness, seizure, motor findings, raised ICP/cerebral edema) not attributable to any other cause. For example, a subject with an ICE score of 3 who has a generalized seizure is classified as having Grade 3 ICANS.
- b A subject with an ICE score of 0 may be classified as having Grade 3 ICANS if the subject is awake with global aphasia. But a subject with an ICE score of 0 may be classified as having Grade 4 ICANS if the subject is unarousable.
- c Depressed level of consciousness should be attributable to no other cause (e.g. no sedating medication).
- d Tremors and myoclonus associated with immune effector cell therapies may be graded according to CTCAE v5.0 but they do not influence ICANS grading.
- e Intracranial hemorrhage with or without associated edema is not considered a neurotoxicity feature and is excluded from ICANS grading. It may be graded according to CTCAE v5.0.

Reference: Lee 2019.

Management of clinical neurotoxicity, i.e., encephalopathy syndrome, status epilepticus, and raised intracranial pressure, should follow current recommendations for CAR-T-cell therapies (Neelapu 2018; Table 3, Table 4, and Table 5) and/or institutional practice.

Table 3	Recommendations for the Management of Encephalopathy Syndrome
Grade	Management
Grade 1	
 
Vigilant supportive care; aspiration precautions; IV hydration
 
Withhold oral intake of food, medicines, and fluids, and assess swallowing
 
Convert all oral medications and/or nutrition to IV if swallowing is impaired
 
Avoid medications that cause central nervous system depression
 
Low doses of lorazepam (0.25–0.5 mg IV every 8 hours) or haloperidol (0.5 mg IV every 6 hours) can be used, with careful monitoring, for agitated subjects
 
Neurology consultation
 
Fundoscopic exam to assess for papilloedema
 
MRI of the brain with and without contrast; diagnostic lumbar puncture with measurement of opening pressure; MRI spine if the subject has focal peripheral neurological deficits; CT scan of the brain can be performed if MRI of the brain is not feasible
 
Daily 30-minute EEG until toxicity symptoms resolve; if no seizures are detected on EEG, continue levetiracetam 750 mg every 12 hours
 
If EEG shows non-convulsive status epilepticus, treat as per algorithm in Table 4
 
Consider anti-IL-6 therapy with tocilizumab 8 mg/kg a IV or siltuximab 11 mg/kg IV, if encephalopathy is associated with concurrent CRS
 

Grade 2	
 
Supportive care and neurological work-up as described for grade 1 encephalopathy
 
Tocilizumab 8 mg/kg a IV or siltuximab 11 mg/kg IV if associated with concurrent CRS
 
Dexamethasone 10 mg IV every 6 hours or methylprednisolone 1 mg/kg IV every 12 hours if refractory to anti-IL-6 therapy, or for encephalopathy without concurrent CRS
 

Table 3	Recommendations for the Management of Encephalopathy Syndrome
Grade	Management
	
 
Consider transferring subject to ICU if encephalopathy associated with Grade ≥2 CRS
 

Grade 3	
 
Supportive care and neurological work-up as indicated for Grade 1 encephalopathy
 
ICU transfer is recommended
 
Anti-IL-6 therapy if associated with concurrent CRS, as described for Grade 2 encephalopathy and if not administered previously
 
Corticosteroids as outlined for Grade 2 encephalopathy if symptoms worsen despite anti-IL-6 therapy, or for encephalopathy without concurrent CRS; continue corticosteroids until improvement to Grade 1 encephalopathy and then taper
 
Stage 1 or 2 papilloedema with CSF opening pressure <20 mmHg should be treated as per algorithm presented in Table 4
 
Consider repeat neuroimaging (CT or MRI) every 2–3 days if subject has persistent grade ≥3 encephalopathy
 

Grade 4	
 
Supportive care and neurological work-up as outlined for Grade 1 encephalopathy
 
ICU monitoring; consider mechanical ventilation for airway protection
 
Anti-IL-6 therapy and repeat neuroimaging as described for Grade 3 encephalopathy
 
High-dose corticosteroids continued until improvement to Grade 1 encephalopathy and then taper; for example, methylprednisolone IV 1 g/day for 3 days, followed by rapid taper at 250 mg every 12 hours for 2 days, 125 mg every 12 hours for 2 days, and 60 mg every 12 hours for 2 days
 
For convulsive status epilepticus, treat as per algorithm in Table 4
 
Stage ≥3 papilloedema, with a CSF opening pressure ≥20 mmHg or cerebral oedema, should be treated as per algorithm in Table 4
 

CAR, chimeric antigen receptor; CSF, cerebrospinal fluid; CRS, cytokine release syndrome; CT, computed tomography (scan); EEG, electroencephalogram; ICU, intensive care unit; IV, intravenous; MRI, magnetic resonance imaging. a Maximum amount of tocilizumab per dose is 800 mg.

Reference: Neelapu 2018.

Table 4 Recommendations for the Management of Status Epilepticus					
Status Epilepticus Type	Management				
Non-convulsive status epilepticus	
 
Assess airway, breathing, and circulation; check blood glucose
 
Lorazepam a 0.5 mg IV, with additional 0.5 mg IV every 5 minutes, as needed, up to a total of 2 mg to control electrographical seizures
 
Levetiracetam 500 mg IV bolus, as well as maintenance doses
 
If seizures persist, transfer to ICU and treat with phenobarbital loading dose of 60 mg IV
 
Maintenance doses after resolution of non-convulsive status epilepticus are as follows: lorazepam 0.5 mg IV every 8 hours for three doses; levetiracetam 1,000 mg IV every 12 hours; phenobarbital 30 mg IV every 12 hours
 
				
Convulsive status epilepticus	
 
Assess airway, breathing, and circulation; check blood glucose
 
Transfer to ICU
 
Lorazepam a 2 mg IV, with additional 2 mg IV to a total of 4 mg to control seizures
 
Levetiracetam 500 mg IV bolus, as well as maintenance doses
 
				

Table 4 Recommendations for the Management of Status Epilepticus					
Status Epilepticus Type	Management				
	
 
If seizures persist, add phenobarbital treatment at a loading dose of 15 mg/kg IV
 
Maintenance doses after resolution of convulsive status epilepticus are: lorazepam 0.5 mg IV every 8 hours for three doses; levetiracetam 1,000 mg IV every 12 hours; phenobarbital 1–3 mg/kg IV every 12 hours
 
Continuous electroencephalogram monitoring should be performed, if seizures are refractory to treatment
 
				

ICU, intensive care unit; IV, intravenous.

NOTE: All indicated doses of medication are for adult subjects.

a Lorazepam is the recommended benzodiazepine because it is short-acting, compared with diazepam, and has been widely used in the management of seizures.

Reference: Neelapu 2018.

Table 5 Recommendation for the Management of Raised Intracranial Pressure (ICP)						
Stage	Management					
Stage 1 or 2 papilledema a with CSF opening pressure of <20 mmHg without cerebral edema	
 
Acetazolamide 1,000 mg IV, followed by 250–1,000 mg IV every 12 hours (adjust dose based on renal function and acid-base balance, monitored 1–2 times daily)
 
					
Stage 3, 4, or 5 papilloedema, a with any sign of cerebral oedema on imaging studies, or a CSF opening pressure of ≥20 mmHg	
 
IV 1 g/day, as recommended for Grade 4 encephalopathy syndrome (Table 3)
 
Elevate head end of the subject's bed to an angle of 30 degrees
 
Hyperventilation to achieve target partial pressure of arterial carbon dioxide (PaCO2) of 28–30 mmHg, but maintained for no longer than 24 hours
 
Hyperosmolar therapy with either mannitol (20 g/dL solution) or hypertonic saline (3% or 23.4%, as detailed below)
 
Mannitol: initial dose 0.5–1 g/kg; maintenance at 0.25–1 g/kg every 6 hours while monitoring metabolic profile and serum osmolality every 6 hours, and withhold mannitol if serum osmolality is ≥320 mOsm/kg, or the osmolality gap is ≥40
 
Hypertonic saline: initial 250 mL of 3% hypertonic saline; maintenance at 50–75 mL/h while monitoring electrolytes every 4 hours, and withhold infusion if serum Na levels reach ≥155 mEq/L
 
For subjects with imminent herniation: initial 30 mL of 23.4% hypertonic saline; repeat after 15 minutes, if needed
 
If subject has ommaya reservoir, drain CSF to target opening pressure of <20 mmHg
 
Consider neurosurgery consultation and IV anesthetics for burst-suppression pattern on electroencephalography
 
					

Table 5 Recommendation for the Management of Raised Intracranial Pressure (ICP)					
Stage	Management				
	
 
Metabolic profiling every 6 hours and daily CT scan of head, with adjustments in usage of the aforementioned medications to prevent rebound cerebral edema, renal failure, electrolyte abnormalities, hypovolemia, and hypotension
 
				

CSF, cerebrospinal fluid; CT, computed tomography (scan); IV, intravenous.

NOTE: All medication doses indicated are for adults.

a Papilledema grading should be performed according to the modified Frisén scale. Reference: Neelapu 2018.

#### 7.5 Tumor Lysis Syndrome (TLS)

TLS is a possible risk associated with anti-tumor therapy however the risk of TLS on this protocol is exceedingly low because patients have received recent highdose chemotherapy and tumor bulk at time of autoHCT is low. TLS symptoms include nausea, vomiting, diarrhea, muscle cramps or twitches, weakness, numbness or tingling, fatigue, decreased urination, irregular heart rate, restlessness, irritability, delirium, hallucinations, and seizures. TLS is comprised of abnormal lab changes that include hyperuricemia, hyperkalemia, hyperphosphatemia, and hypocalcemia.

Prophylaxis for and management of TLS should be done in accordance with standard institutional practice.

## 7.6 Myelosuppression, Immunosuppression, Bone Marrow Failure, and Infections

Therapies used for the treatment of hematologic malignancies have been reported to cause myelosuppression (neutropenia and/or thrombocytopenia), leukopenia, anemia; and in some cases, bone marrow failure. Hematologic cytopenias could be further compounded by other factors such as underlying disease, concurrent illnesses and concomitant medications.

Close monitoring of complete blood count (CBC) and for the development of infections is strongly recommended. In general, management including transfusion support and use of growth factors, should be done in accordance with standard institutional practice.

#### Non-engraftment

We will collect detailed data on hematologic toxicity in Component 1 and will provide FDA with safety data for discussion before proceeding with Component 2 if any Grade 4 hematologic toxicity occurs. Therefore, we will gain safety data on FT596 and expect that the risk of non-engraftment in Component 2 will be low. Non-engraftment by Day 28 will be confirmed by bone marrow biopsy (defined as <5% marrow cellularity). To mitigate the adverse outcome, all subjects in

Component 2 will undergo HLA typing and search for an allogeneic donor (related sibling, haplo-donor or unrelated donor) for potential rescue allogeneic donor hematopoietic cell transplantation.

### 8 Schedule of Treatment, Tests, and Procedures

If a patient is consented after the transplant procedure, initial inclusion and exclusion criteria is abstracted for the standard of care assessment prior to transplant as permitted in the patient consent form document. No research related procedures or sample collections are permitted prior to consent signing.

For scheduling purposes, the rituximab/FT596 "package" is administered with a +3 day window from the targeted FT596 administration day (Day 30 or Day 7 post-transplant). Rituximab or an FDA approved biosimilar is given 2 to 3 days (48 to 72 hours) prior to the planned FT596 infusion.

In the event of rituximab related toxicity, the FT596 infusion may delayed for up to 7 days to permit resolution of any related adverse events to Grade 1 or better.

A  $\pm$  1 Day window is permitted for visits through the End of Treatment (EOT) visit; however, whenever feasible do not shift subsequent time points off of the targeted day (based on the actual day of the FT596 infusion).

After the EOT visit, follow-up for this study will coincide with the standard of care transplant follow-up schedule through 1 year post-transplant.

In addition, targeted days may be altered as clinically appropriate.

### 8.1 Required Clinical Care Evaluations

	Screening prior to	Post-Transplant Confirmation of	Day of FT596	Post FT596 Infusion (using Day 0 as the day of infusion)				Abstract from patient's EMR at	3, 6, and 12 months from		
	Transplant	Continuing Eligibility (approximately Day 21 for Component 1)	approved biosimilar, e.g. Truxima and Ruxience) Infusion (-3 day window for labs and assessment)	Infusion (Day 0^)	day 2	day 7	day 14	day 21	EOT visit day 28	each SOC visit until the 3 month post-transplant	transplant at the time of SOC visit
Consent	X 		-								
Screening Assessment	Х										
Brief Medical Assessment				Х	Х	Х	Х	Х	Х		
Medical History	Х	Х									Х
Concomitant Medications	Х			Х							
Assess Venous Access		Х									
Physical Exam	Х	Х	Х								Х
ICANS (neurotoxicity) monitoring – refer to Section 7.4		X		Х		X 	X 	X 	X 		X
Weight	Х	Х	X								
Height	Х										
Vitals and Pulse Oximetry	Х	Х	X	Х					X 		
Toxicity Assessment	Х	Х	Х	Х	Х	Х	Х	Х	Х	Х	Х
CBC, diff, plt	Х	Х	X	Х	Х	Х	Х	Х	Х	Х	Х
Basic metabolic panel (BMP) 				Х	Х	Х	Х	Х			Х
Comprehensive metabolic panel (CMP) or equivalent  plus magnesium, phosporus	X	X	X						X	X	
eGFR	Х	Х									
Urine or serum pregnancy test for WOCBP 	х	X									
If pt develops cytokine release syndrome (CRS): CRP, ferritin and, if testing available, IL-6				If CRS is s At diagnos outpt visit t	uspecter is docun until reso	d obtain nent CR plution of	CRP, ferr P, ferritin a CRS. Re	itin and IL- and IL-6 lev fer to Secti	6 levels vels 3 x week on 7.3.	ly if inpt or at every	
If pt develops neurotoxicity				Refer to Se	Section 7.4 for FDA recommended testing 						

	Screening prior to	Post-Transplant Confirmation of	Day of Rituximab Day of Rituxan or an EDA ET59		Day of Post FT596 Infusion (using Day 0 as the day of infusion)			Abstract from patient's EMR at	3, 6, and 12 months from		
	Transplant	Continuing Eligibility (approximately Day 21 for Component 1)	approved Infusion biosimilar, e.g. (Day 0^) Truxima and Ruxience) Infusion (-3 day window for labs and assessment)	day 2	day 7	day 14	day 21	EOT visit day 28	each SOC visit until the 3 month post-transplant	transplant at the time of SOC visit	
Disease staging	Х	Х									Per SOC
CXR or chest CT scan	X										
PFTs⁵	Х										
EKG	Х										

^ *day* 0 is assigned to the day of the FT596 infusion regardless of whether the infusion is given Day 30 or Day 7 post-transplant

1 Consent is obtained prior to transplant – no re-consent required

2 basic metabolic panel consists of BUN, creatinine, calcium, glucose, lytes (CO2, Cl, Na, K)

3 comprehensive metabolic panel consists of albumin, alkaline phosphatase (ALP), alanine aminotransferase (ALT), aspartate aminotransferase (AST), blood urea nitrogen (BUN), calcium, creatinine, glucose, lytes (CO2, Cl, Na,, K), total bilirubin, and total protein

4 women of child bearing potential

5 pulmonary function testing required only if symptomatic or prior known impairment

6 Vital signs (temperature, systolic and diastolic blood pressure, heart rate, and respiration rate) are performed in association with the FT596 infusion at the following time points: within 15 minutes of the infusion start, at 10 (±5) minutes during infusion, and every 15 (±5) minutes for 1 hour after the end of the last administered bag of FT596.

7 If the patient develops neurological toxicity for which cerebrospinal fluid (CSF) analysis is performed, in addition to standard clinical testing, the sample should be tested for Human Herpes Virus (HHV 6&7) per Section 7.4. In addition, quantitative testing in blood for HHV6 and HHV7 in the context of neurotoxicity should be done. I

8 Long-term follow-up continues for up to 15 years per CPRC 2020LS052

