#### 4.3 Confirmation of Continuing Eligibility Post-Transplant

- No life-threatening medical issues (i.e. ongoing Grade 4 adverse events) where, in the opinion of the treating investigator, use of FT596 is not in the patient's best interest.
- No active uncontrolled infection
- Adequate organ function post-transplant including:
  - alanine aminotransferase (ALT) and aspartate aminotransferase (AST) ≤5 x ULN (Grade 2 CTCAE v5)
  - total bilirubin ≤1.5 x ULN (Grade 1 CTCAE v5)
  - serum creatinine ≤1.5 x ULN (Grade 1 CTCAE v5)
  - oxygen saturation ≥93% on room air
- For Day 30 dosing only CBC requirement consistent with engraftment (ANC>500, platelet>20,000 without transfusion support within previous 7 days). There are no CBC parameters for Day 7 dosing.
- No requirement for systemic immunosuppressive therapy (> 5mg prednisone daily) during the FT596 dosing period.

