#### FT596 may be delayed for up to 3 days for these events to resolve.

#### 5 Patient Screening and Enrollment

For the majority of participants, consent for this study will be presented as part of the pre-transplant discussion as research related samples are collected before beginning of conditioning chemotherapy.

Alternatively, a patient also may be consented and enrolled after transplant provided the patient 1) can begin treatment within their assigned window, 2) they meet all of the inclusion criteria and none of the exclusion criteria based on the previously documented standard of care pre-transplant assessment and 3) meet the post-transplant requirements found in Section 4.3. Research related procedures and sample collections missed due to late consenting are not protocol deviations.

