#### **12 Statistical Considerations**

#### 12.1 Study Designs

This study consists of two components. The 1st component is a Phase I clinical trial to identify the maximum tolerated dose (MTD) of FT596 at Day 30 post FT596 infusion. The second component is a Phase I clinical trial to identify the MTD of FT596 at Day 7 post FT596 infusion. Rituximab is given 2-3 days before FT596. In addition to identifying the MTD and providing preliminary estimates of safety, secondary objectives include providing preliminary descriptive estimates of efficacy such as progression-free survival, relapse and non-relapse mortality along with their error measurements. Correlative objectives include measurement of the persistence of FT596 in blood after each FT596 infusion by immunophenotyping and PCR up to 1 year, the association of FT596 persistence with safety and anti-tumor activity.

Component 1 will identify the MTD of FT596 when given as a single dose at Day 30. Up to three FT596 dose levels are planned (Dose Level 1:  $9x10^7$  cells/dose, Dose Level 2:  $3x10^8$  cells/dose, Dose Level 3:  $9x10^8$  cells/dose with a Dose Level - 1:  $3x10^7$  cells/dose tested only if DLT at DL1).

**Component 1 dose limiting toxicity** is defined as any of the following events within 28 days after the FT596 dosing based on CTCAE v5:

- Grade 4 hematologic toxicity lasting > 7 days (not including lymphopenia)
- Grade 4 non-hematologic toxicity
- Grade ≥3 FT596 Infusion Related Reaction
- Grade 2 acute GVHD that requires steroid therapy >7 days or progression after 3 days of steroids or has partial response after 14 days of treatment
- Grade ≥3 acute GVHD
- Grade 4 cytokine release syndrome (CRS)
- Grade 3 CRS that does not resolve to < Grade 2 in 72 hours
- Grade 3 neurotoxicity

- Grade 3 organ toxicity involving vital organs; cardiac, central nervous system and pulmonary that lasts for longer than 7 days including Grade 3 Investigations (laboratory values) of any duration that indicate damage to vital organs.
- Any Grade 3 non-hematological toxicity that does not resolve to ≤Grade 2 within 72 hours; excepting Grade 3 renal and hepatic toxicity which may take up to 7 days to resolve to ≤Grade 2

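### No liver test is scheduled between the rituximab-day panel and Day 28, so a hepatic DLT that comes and goes inside the DLT window can be missed unless routine care happens to draw one

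*Combined protocol and SAP*

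**What the plan says.** The table in Section 8.1 has two chemistry rows. Read by column, the row headed "Comprehensive metabolic panel (CMP) or equivalent" is marked at screening, post-transplant confirmation of eligibility, the rituximab day, the end-of-treatment visit on Day 28, and the column for abstraction from the medical record. The basic-panel row is marked on FT596 Day 0, Days 2, 7, 14 and 21, and at 3, 6 and 12 months.

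The footnotes define the contents. The basic panel: "basic metabolic panel consists of BUN, creatinine, calcium, glucose, lytes (CO2, Cl, Na, K". The comprehensive panel: "comprehensive metabolic panel consists of albumin, alkaline phosphatase (ALP), alanine aminotransferase (ALT), aspartate aminotransferase (AST), blood urea nitrogen (BUN", continuing to total bilirubin. Only the second contains liver tests. The rituximab-day column allows a minus "3 day window for labs and assessment".

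The DLT list in Section 12.1 covers 28 days after FT596. It includes any Grade 4 non-hematologic toxicity. It also includes any Grade 3 non-hematologic toxicity not resolved within 72 hours, "excepting Grade 3 renal and hepatic toxicity which may take up to 7 days to resolve to ≤Grade 2".

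Section 4.3 sets the post-transplant liver limits: "alanine aminotransferase (ALT) and aspartate aminotransferase (AST) ≤5 x ULN (Grade 2 CTCAE v5", and total bilirubin at most 1.5 x ULN. The line that closes that list, printed just above the Section 5 heading, adds: "FT596 may be delayed for up to 3 days for these events to resolve".

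**The concern.** DLT is the primary endpoint and the only toxicity input to the CRM. Two hepatic events count: a Grade 4 value of any duration, and a Grade 3 value that persists beyond 7 days. Both are laboratory findings that may cause no symptoms, so they are reliably seen only if ALT, AST and bilirubin are measured. The schedule measures them at one of the six visits from Day 0 to Day 28.

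A DLT that is not observed enters the CRM as a patient without toxicity. That lowers the estimated toxicity at every dose level and favors escalation. If it occurs at Dose Level 1, it also removes the trigger for Dose Level -1, which is tested only after a DLT at Level 1. A missed Grade 4 value would not count toward the halt after two Grade 4 DLTs in Section 12.4.4. Section 7 says there are no clinical data on FT596, so the plan has no clinical record from which to presume that the liver is unaffected.

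There is also a smaller point about eligibility. Day 0 re-measures creatinine, blood counts and pulse oximetry, but not the liver values. The rule allowing FT596 to wait for the 4.3 events to resolve has no liver retest attached to it.

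**Working it through.** The plan states no figure for this point, so there is none to reproduce.

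**1. Age of the last scheduled liver panel at infusion.** Inputs: rituximab 2-3 days before FT596 (Sections 6 and 8), laboratory window up to 3 days before rituximab (8.1), FT596 not given later than 7 days after rituximab (6.6).
- Usual case: 2 + 0 = 2 days to 3 + 3 = 6 days.
- FT596 held for rituximab toxicity, per 6.6: up to 7 + 3 = 10 days.
- If the 7-day delay in 6.1.2 and 8 is read as added to the 2-3 days: up to 3 + 7 + 3 = 13 days.

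**2. Gap to the next scheduled liver panel.** The Day 28 visit has a window of 1 day either side (Section 8), so it falls on Days 27-29.
- Usual case: 2 + 27 = 29 days to 6 + 29 = 35 days.
- With delay: up to 10 + 29 = 39 days, or 13 + 29 = 42 days on the alternative reading.

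**3. Which episodes meet a scheduled draw.** Assumptions: onset day u is equally likely on each of Days 1-28, the abnormal value lasts D days (Days u to u + D - 1), visits are on schedule, and no standard-of-care liver test is drawn. The Day 28 draw meets the episode when u ≤ 28 ≤ u + D - 1, which holds for D of the 28 onset days (D ≤ 28).

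| D (days) | Day 28 only | Days 2, 7, 14, 21 and 28 | At least two draws, same five days |
|---|---|---|---|
| 8 | 8/28 = 29% | 28/28 | 5/28 |
| 10 | 10/28 = 36% | 28/28 | 11/28 |
| 14 | 14/28 = 50% | 28/28 | 21/28 |

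An 8-day episode starting on any of Days 1-20 ends by Day 27 and meets no scheduled liver draw (0/20). A single draw can never show that a value lasted more than 7 days.

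**4. What one missed DLT does to the model.** Inputs from Section 12.1: power model p_i^exp(α), skeleton 1%, 3%, 6%, α normal with mean 0 and variance 2, target 25%. I take the posterior mean of α, insert it in the power model, and choose the dose closest to target.
- Dose Level 1, 1 DLT in 3: posterior mean of α is -1.262, and 0.01^exp(-1.262) = 27%. The model stays at Level 1.
- Same cohort with that DLT unobserved, 0 in 3: posterior mean of α is 0.522, and 0.01^exp(0.522) = 0.04%. The model escalates.
- Level 1 0/3 and Level 2 2/3: posterior mean of α is -1.171, giving 24% at Level 1 and 34% at Level 2. The model returns to Level 1.
- Same data with one of the two unobserved: posterior mean of α is -0.713, giving 10%, 18% and 25.2%. The closest dose is Level 3. If 25% is applied as a strict ceiling, it is Level 2. Either way the assignment is higher than with the full data.

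Averaging the probability itself over the posterior, instead of inserting the mean of α, gives 29% and 4.0% for the first pair. The contrast is the same.

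**The case against.** The strongest reply is that the schedule is a minimum and not the only source of data. Toxicity assessment is marked at every visit in 8.1, and DLT assessment is listed repeatedly in 8.2. The table in 10.2 requires Grade 2 and higher events to be documented from rituximab through end of treatment. Patients are in standard post-transplant care, so a liver test drawn for clinical reasons would reach the DLT record. This stands as a limit on the claim. A reader might infer that an asymptomatic hepatic DLT will be recorded as a non-event; the documents support only that it can be missed if no routine test is drawn. They do not give the frequency of routine testing, so the true detection rate is unknown and may differ between sites.

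The medical-record column carries a comprehensive-panel mark and states no start date. Its position after Day 28, and the statement in Section 8 that follow-up joins the standard schedule after end of treatment, suggest that it covers the later period, though they do not settle it. In either case, abstracting results does not require a test.

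A reader might also infer that the 4.3 liver limits cannot be confirmed for infusion. The documents do not support that. Sections 4.3 and 5.2 place the check after transplant and before assignment to treatment. A comprehensive panel is scheduled at that visit and again on the rituximab day, and nothing asks for same-day confirmation. What remains is that the values are not re-measured on Day 0, and that a delay for resolution has no scheduled liver retest.

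Finally, weekly draws do not time a 7-day criterion exactly. That is correct, and the fix allows for it.

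**Conclusion.** The point holds in this limited form. Protocol-required testing leaves 29-35 days between liver panels in the usual case (up to 39, or 42 on one reading, with delay), and that gap covers nearly all of the 28-day DLT window. The Day 28 sample alone meets 29%, 36% and 50% of 8-, 10- and 14-day episodes, and by itself cannot establish duration. These percentages rest on uniform onset, chosen durations and no standard-of-care liver testing. They show what the schedule can see and do not predict events missed.

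The direction of the error is clear: an unobserved DLT lowers the CRM estimates, and one at Dose Level 1 is enough to turn a decision to stay into a decision to escalate. How often this would happen cannot be calculated, because the documents give no hepatic event rate. The eligibility part is a gap in re-measurement, normally of 2-6 days, and does not show that patients would be infused outside the limits.

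**What to change.** In 8.1, run the comprehensive panel in place of the basic panel on Day 0 and Days 2, 7, 14 and 21. It contains everything in the basic panel and uses blood already drawn at existing visits. On-schedule visits would then meet every episode of 8 days or longer with onset on Days 1-28. Visits shifted within the 1-day window can be up to 7 + 2 = 9 days apart, so the guarantee is for on-schedule visits only.

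In 12.1, state how resolution within 7 days is documented for a Grade 3 liver value, since weekly draws only bracket it. Say also how a value first seen at Day 28 is classified.

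Reconcile 4.3 and its delay line with 8.1, so that it is clear when the liver limits are to be verified and which test serves that purpose during a delay. This asks for consistency between the sections and does not propose a new rule for giving FT596. State also whether the medical-record column applies before Day 28.

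The cost is a slightly higher laboratory charge at five visits and a few sentences of text.
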